Full study protocol and statistical analysis plan

Official Title of the study:

Analysis of maternal plasma/urine/hair magnesium and vanadium levels in preeclampsia

Date of the document:

May 2020.

Contents:

1. Participant Flow
2. Baseline Characteristics
3. Outcome Measures
4. Endpoints of the study
5. Limitations and Strengths
6. Certain Agreements
7. Results Point of Contact

1. Participant Flow

Recruitment Details

This observational case-control study will be conducted at the Department of Obstetrics and Gynecology, Cengiz Gokcek Public Hospital, Gaziantep, Turkey, between May 2020 and February 2021. The protocol was approved by the Ethics Committee for Clinical Research of Gaziantep University (reference no: 2020/130). The study strictly will be adhered to the principles of the Declaration of Helsinki. All subjects will be included in the study gave oral and written informed consent. Two-hundred ten women will be enrolled in the study in two groups.

The investigators included subjects consisted of women with a singleton pregnancy who were diagnosed as having late-onset preeclampsia between 34+0 and 41+0 weeks of gestation. Pregnant women with uncomplicated pregnancies were randomly selected to serve as controls. Other participants with healthy volunteer women as control non-pregnant group. The study population will have consisted of 70 late-onset preeclampsia patients as a study group, 70 participants with normal pregnancies as control pregnant group and 70 participants with healthy volunteer women as control non-pregnant group. All participants included in the study gave oral and written informed consent.

Pre-assignment Details

The authors firstly were assessed the recruited people to ensure meeting the inclusion and exclusion criteria. The inclusion criteria were made according to the official documents.

Arm/Group Information *

There are three groups in the study.

Arm/Group Title *

Preeclampsia group

Control pregnant group

Control non-pregnant group

2. Baseline Characteristics

To detect significant difference between groups according to variable with a moderate effect size (Cohen's $d = 0.5$), minimum required sample size was estimated as 63 for each group ($\alpha=0.05$, $1-\beta=0.80$). Power analysis was performed by using G power package version 3.1. SPSS for Windows 22.0 and Medcalc programs will be used for statistical analysis. $p<0.05$ will be accepted as statistical significance.

3. Outcome Measures

The primary outcome in these analyses will be compare magnesium and vanadium levels in LOPE group and the control groups. The secondary outcome will be compare the magnesium and vanadium levels in mild LOPE group and severity LOPE group. Tertiary outcome will be compare the magnesium and vanadium levels in SGA group and non-SGA group. Venous blood sampled from the antecubital veins for measuring plasma concentration of cadmium, lead and vanadium levels. The three metals (cadmium, lead and vanadium) were measured using inductively coupled plasma-mass spectrometry (Thermo Scientific ICAPQc, USA).

4. Endpoints of the study:

The primary outcome in these analyses will be compare magnesium and vanadium levels in LOPE group and the control groups. The secondary outcome will be compare the magnesium and vanadium levels in mild LOPE group and severity LOPE group. Tertiary outcome will be compare the magnesium and vanadium levels in SGA group and non-SGA group.

5. Limitations and strengths:

Because our study is observational, we could not eliminate the possibility of unmeasured and/or residual confounding of the reported associations. . These metals will be measured blood, urine and

hair samples. So, these measurements may not reflect the metals exposure levels only recent exposure and will reflect before and during pregnancy.

6. Certain Agreements

This work will be supported by the Scientific Research Project Fund of Yozgat Bozok University.

7. Results Point of Contact

Corresponding Author: [name], Department of Obstetrics and Gynecology, Cengiz Gokcek Women's and Children's Hospital, Gaziantep, Turkey, [contact]

Address: [name]

GSM: [contact]

[contact]

[contact]

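### No gestational-age window, matching or adjustment is stated for the pregnant controls, so a gap from the 34+0 to 41+0 week cases could bias the LOPE versus normal-pregnant comparison in either direction

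*Combined protocol and SAP*

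**What the plan says.** Section 1 (Participant Flow) defines the cases as singleton pregnancies "diagnosed as having late-onset preeclampsia between 34+0 and 41+0 weeks of gestation". The rule for the pregnant controls follows directly: "Pregnant women with uncomplicated pregnancies were randomly selected to serve as controls". The only other description of that group is its size, "70 participants with normal pregnancies as control pregnant group". No sampling frame, gestational-age range or matching variable is attached to it.

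Eligibility is not listed. Under Pre-assignment Details the document says "The inclusion criteria were made according to the official documents", and those documents are neither identified nor reproduced.

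Section 3 (Outcome Measures), repeated in section 4, gives the analysis that depends on these controls: "The primary outcome in these analyses will be compare magnesium and vanadium levels in LOPE group and the control groups". Section 2 adds a sample size, the software and a 5% significance level, but no test, model or covariate. Gestational age at sampling is stated for neither pregnant group; the case window refers to diagnosis. Section 5 carries a general caveat, "we could not eliminate the possibility of unmeasured and/or residual confounding of the reported associations", which names no variable and no remedy.

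**The concern.** One pregnant group has a gestational-age range and the other has none. Random selection reproduces the pool it draws from. If that pool is all uncomplicated pregnancies at the hospital, nothing makes its gestational ages resemble those of women diagnosed from 34+0 weeks onward. Controls could be earlier on average (antenatal clinic attenders, for example) or later (women admitted at term).

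If magnesium or vanadium changes with gestational age, the difference between LOPE and normal pregnancy contains a term equal to the slope times the gap. That term can create a difference or hide one, and a larger sample does not remove it. The dependence may also differ between plasma, urine and hair, the three sample types in the title, so the bias need not be the same for each measurement.

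The reach is limited:
- **Affected:** the LOPE versus normal-pregnant part of the primary outcome.
- **Possibly affected:** the tertiary SGA versus non-SGA comparison, whose population is not stated, if it includes pregnant controls.
- **Not affected:** LOPE versus non-pregnant women, and the secondary comparison ("The secondary outcome will be compare the magnesium and vanadium levels in mild LOPE group and severity LOPE group"). Neither depends on how pregnant controls are selected.

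**Working it through.** **1. The plan's own figure.** Section 2 sizes the study as follows: "To detect significant difference between groups according to variable with a moderate effect size", with d = 0.5, alpha 0.05 and power 0.80, giving 63 per group. Sidedness is not stated; two-sided is assumed because it reproduces the figure. The normal approximation is n = 2(z₀.₉₇₅ + z₀.₈₀)²/d² = 2(1.960 + 0.842)²/0.25 = 62.8, so 63. The t-test version gives 64. The figure is sound, but it presumes an unbiased comparison.

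**2. Baseline at the planned size.** With 70 per group (section 1), the noncentrality is d√(n/2) = 0.5 × √35 = 2.958 on 138 degrees of freedom, with critical value 1.977. Power is 83.6%.

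**3. Adding a gestational-age shift.** Let s be the change in metal level per week, in SD units, and g the difference in mean gestational age at sampling in weeks. The bias is b = s × g. With no true difference, the false-positive rate is the two-sided noncentral-t rejection probability at b√35. With a true d of 0.5 and an opposing bias, power is the same probability at (0.5 − b)√35. The documents give neither s nor g, so both are assumptions, and each slope is held constant across gaps so that the rows are comparable.

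False-positive rate (nominal 5%):

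| Assumed slope | Gap 1 week | Gap 2 weeks | Gap 3 weeks |
|---|---|---|---|
| 0 | 5.0% | 5.0% | 5.0% |
| 0.02 SD/week | 5.2% | 5.6% | 6.4% |
| 0.05 SD/week | 6.0% | 9.0% | 14.3% |
| 0.10 SD/week | 9.0% | 21.7% | 42.2% |

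Worked cell: 0.05 × 2 = 0.10 SD; 0.10 × √35 = 0.592; rejection probability 9.0%.

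Power for a true d of 0.5 with opposing bias at 0.05 SD/week: 75.3% (d − b = 0.45), 65.2% (0.40) and 53.8% (0.35), against 83.6% with no bias. The sign of the gap does not change the false-positive rate. Whether the bias masks or exaggerates a true difference depends on the signs of the slope, the gap and the true effect.

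**4. Comparing the remedies.** Assume gestational age at sampling is uniform on 34 to 41 weeks in cases and on L to 41 weeks in controls. The gap is then (34 − L)/2. Adjusting for gestational age multiplies the variance of the group effect by VIF = 1 + gap²/4, with the gap in pooled SDs. If r is the within-group correlation between metal level and gestational age, the standardised effect becomes 0.5/√(1 − r²), tested on 137 degrees of freedom. All rows use r from 0 to 0.4.

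| Controls | Gap | VIF | Power, adjusted |
|---|---|---|---|
| Matched, 34–41 weeks | 0 | 1.00 | 83.6–89.3% |
| From 32 weeks, unmatched | 1 week (0.43 SD) | 1.05 | 81.9–88.0% |
| From 30 weeks, unmatched | 2 weeks (0.75 SD) | 1.14 | 78.5–85.1% |
| From 28 weeks, unmatched | 3 weeks (1.00 SD) | 1.25 | 74.8–81.8% |

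The ranges overlap because each spans the same values of r. At any given r, matching plus adjustment has the highest power.

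**The case against.** **A control window may already exist.** Eligibility is deferred to documents not supplied here. This stands. A reader might infer that the controls will be unmatched, or that their gestational ages will differ from those of the cases; the document supports neither. It supports only that no window, matching or adjustment is stated in it.

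**The size is assumed.** This also stands. With no slope there is no bias, and at 0.02 SD per week even a 3-week gap gives only 6.4%. The 42.2% figure needs the steepest slope and the widest gap together, and should not be read as an expected error rate.

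**Diagnosis is not sampling.** The 34+0 to 41+0 range is given for diagnosis, so placing cases in that range at sampling is an approximation. It enters only the comparison of remedies, not the false-positive table.

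**The primary outcome may not be two separate contrasts.** The wording could also mean an overall or a pooled comparison. That is fair, but the normal-pregnant group is part of the comparison on each reading.

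**Random selection and the section 5 caveat already deal with it.** They do not. Random sampling from an undefined pool does not align controls with cases, and a general caveat does not control a confounder that can be recorded at sampling and balanced by design.

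**Matching plus regression is more than the defect strictly requires.** In part this is so: a stated window with pre-specified adjustment would deal with most of the problem. The reason for matching as well is the power shown in step 4. A shared window alone also does not guarantee equal gestational ages within it.

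**Conclusion.** The point holds as a conditional one. The stated selection rule, followed literally, permits a gestational-age gap between cases and pregnant controls, and nothing stated in the document removes its effect. If a metal level varies with gestational age, the LOPE versus normal-pregnant comparison would be biased. The tertiary SGA comparison could be biased too, if it includes pregnant controls.

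Neither size nor direction can be fixed from the documents. Over the assumed slopes of 0.02 to 0.10 SD per week and gaps of 1 to 3 weeks, the false-positive rate runs from 5.2% to 42.2%. A reader might take this as evidence that the primary result will be wrong. The documents do not show that, because they contain no slope, no gap and no control window. The change is worth making because it is cheap and because matching has to be set before controls are enrolled.

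**What to change.** In section 1, select pregnant controls from 34+0 to 41+0 weeks, frequency-matched to cases by gestational week at sampling. Record gestational age at sampling in both pregnant groups.

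In the analysis text, pre-specify that the LOPE versus normal-pregnant comparison is adjusted for it, by linear regression with group and gestational age at sampling. Report the non-pregnant contrast separately without this covariate, since gestational age does not apply to that group. State whether the SGA comparison includes pregnant controls.

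If the external eligibility documents already set a control window, state it here and add the matching or the adjustment.

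**Cost:** a few sentences, one recorded variable, slightly slower control recruitment and one degree of freedom. On the assumptions in step 4, power for d = 0.5 at 70 per group is about 84–89% with matching and adjustment. Adjustment alone gives 82–88%, 79–85% or 75–82% if controls start at 32, 30 or 28 weeks. No increase in sample size is needed.

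### Do equal arms of 70 shortchange the mild versus severe LOPE comparison, so that 84/63/63 should replace 70/70/70?

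*Combined protocol and SAP*

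**What the plan says.** Section 1 (Participant Flow) sets the group sizes: "The study population will have consisted of 70 late-onset preeclampsia patients as a study group", together with "70 participants with normal pregnancies as control pregnant group and 70 participants with healthy volunteer women as control non-pregnant group", 210 women in all. Recruitment is at one hospital between May 2020 and February 2021.

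Section 2 (Baseline Characteristics) holds the only sample-size calculation. For a standardised difference of d = 0.5, alpha 0.05 and power 0.80, the "minimum required sample size was estimated as 63 for each group".

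Sections 3 and 4 list the outcomes. On the primary one: "The primary outcome in these analyses will be compare magnesium and vanadium levels in LOPE group and the control groups". On the secondary one: "The secondary outcome will be compare the magnesium and vanadium levels in mild LOPE group and severity LOPE group".

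The document does not give a target difference, a power or an expected split for mild versus severe, and it does not explain why the arms are equal or why 70 was chosen rather than 63. It names no test and does not say whether testing is one- or two-sided.

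**The concern.** The LOPE group does more work than either control group. It enters both LOPE-versus-control contrasts and is then divided again by severity. Each control group enters only one LOPE-versus-control contrast, yet has 7 women above the stated minimum of 63. When one arm is shared between comparisons, equal arms are usually not the most efficient split. Moving 7 women from each control group to LOPE appears to improve the primary and the secondary outcome at no cost in total numbers.

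The secondary comparison is also weak. If the plan's d = 0.5 is applied to it, power is little better than even in the best case and lower when the severity split is uneven. A non-significant result could then be misread as showing that mild and severe disease do not differ in magnesium or vanadium.

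**Working it through.** **Inputs.** From the document: alpha 0.05, power 0.80, d = 0.5, 63 required per group, 70 per group planned, 210 in total. Assumed: a two-sided two-sample t test, no lost samples, and a range of mild:severe splits.

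**The plan's own figure.** With the normal approximation, n per group = 2(1.960 + 0.842)²/0.5² = 62.8, which rounds up to 63. This matches the document. The noncentral t gives 64, and 63 per group then has 79.5% power. One-sided testing would give 50 or 51, so the plan's figure points to two-sided testing.

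**Power formula.** For group sizes n1 and n2, the noncentrality is d·√(n1·n2/(n1+n2)) on n1+n2−2 degrees of freedom. Power is the probability that a noncentral t variable with these parameters exceeds the two-sided 5% critical value in absolute size.

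**Primary outcome, LOPE versus one control group, d = 0.5**

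| LOPE / control | Noncentrality | Power |
|---|---|---|
| 70 / 70 (plan) | 0.5·√35 = 2.958 | 83.6% |
| 84 / 63 | 0.5·√36 = 3.000 | 84.6% |
| 79 / 63 | 2.960 | 83.6% |
| 78 / 63 | 2.952 | 83.4% |
| 70 / 63 | 2.879 | 81.5% |

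The planned 70 per group exceeds the stated 63 and gives more than the stated 80%. The alternative gains 1.0 percentage point if all 84 cases are found. With controls set at 63, 79 LOPE women are needed to match the current plan. If only the 70 now planned are recruited, primary power is 2.1 points lower than under the plan (81.5% against 83.6%).

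**Secondary outcome, mild versus severe, if d = 0.5 is borrowed for it**

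| Split | 70 LOPE | 84 LOPE |
|---|---|---|
| even | 35/35: 54.1% | 42/42: 62.0% |
| 2:5 | 20/50: 46.1% | 24/60: 53.4% |
| 1:6 | 10/60: 30.3% | 12/72: 35.4% |

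The gain is 5 to 8 points, and no entry comes near 80%. Even with a perfectly even split, 80% power at d = 0.5 would take 64 women in each severity group, or 128 LOPE women.

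**What the alternative costs.** Going from 70 to 84 cases is 14/70 = 20% more. Over ten months that is 8.4 instead of 7 a month, and the document gives no case volume to show whether this is achievable. Both control groups would sit exactly at 63, so one unusable control sample would put a group below the plan's own minimum. The contrast between the two control groups would fall from 83.6% to 79.5% power.

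**The case for a change.** The strongest case for the concern is that, at a fixed total of 210, 84/63/63 beats 70/70/70 for LOPE versus control under several readings of the primary outcome. Pairwise power rises from 83.6% to 84.6%, power against the pooled controls from 92.5% to 94.2%, and power of a three-group omnibus test with LOPE 0.5 SD from both controls from 86.9% to 89.4%. Pairwise power peaks near 87 LOPE women, so 84 is close to the optimum. By the 80% power criterion, tolerance to lost control samples is also unchanged: a control group can fall to 59 from 70, or to 52 from 63, which is 11 losses either way. The loss of power between the two control groups matters little, because no listed outcome clearly asks for that contrast.

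All of this stands as arithmetic, but it depends on recruiting the extra cases. The tolerance figure, for example, assumes all 84 LOPE women are enrolled with usable samples. Cases must present with the disease at one hospital within a fixed period, whereas controls are selected or volunteer, so a shortfall is a more obvious risk for cases than for controls. The 7-woman margin could be an allowance for losses, although the document does not say so.

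It is also true that d = 0.5 is the plan's only effect size and that mild versus severe is imprecise. Stating the detectable difference (about 0.68 at 80% power for 35/35, 0.97 for 10/60) and reporting a 95% confidence interval would help a reader. That is added detail, and it requires no change to the group sizes.

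**Conclusion.** The concern does not hold. The plan's one sample-size figure reproduces, the planned 70 per group exceeds it, and LOPE versus each control group has 83.6% power at d = 0.5. The plan makes no power claim for mild versus severe LOPE that could be contradicted, and a secondary outcome need not carry 80% power.

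The proposed 84/63/63 is an optional rebalancing. At best it adds 1.0 point to the primary comparison and 5 to 8 points to the secondary one, which stays at 62% or less. Below 79 LOPE women it makes the primary comparison worse than it is now. Choosing equal arms under these conditions is a defensible design decision.

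The power figures assume two-sided t tests, and those for mild versus severe also assume d = 0.5, which the plan does not set for that comparison. The normal approximation shifts the main figures by about one point or less and leaves the conclusion unchanged: 70/70 84.1%, 84/63 85.1%, 35/35 55.2%, 42/42 63.0%.

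### The plan lists no baseline covariates to record and pre-specifies neither matching nor adjustment, so the primary comparisons of non-randomised groups are open to confounding

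*Combined protocol and SAP*

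**What the plan says.** Section 1 describes the design: "This observational case-control study will be conducted at the Department of Obstetrics and Gynecology". The planned groups are "70 late-onset preeclampsia patients as a study group, 70 participants with normal pregnancies as control pregnant group and 70 participants with healthy volunteer women". On the choice of pregnant controls it says "Pregnant women with uncomplicated pregnancies were randomly selected to serve as controls". The non-pregnant controls are healthy volunteers. No matching variable is named for either control group. Section 1 also says that recruits were checked against inclusion and exclusion criteria drawn from official documents, but it does not list those criteria.

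Section 2, headed Baseline Characteristics, gives the sample-size reasoning ("To detect significant difference between groups according to variable with a moderate effect size", Cohen's d = 0.5, with "minimum required sample size was estimated as 63 for each group"), the software, and the p<0.05 threshold. It names no participant characteristic.

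Sections 3 and 4 give the primary outcome as a comparison of magnesium and vanadium between the LOPE group and the control groups. No test, model or covariate is named.

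Section 5 concedes that, the study being observational, "we could not eliminate the possibility of unmeasured and/or residual confounding of the reported associations". It gives no step to measure or control confounding.

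**The concern.** The three groups are not formed by randomisation. Drawing pregnant controls at random makes them representative of uncomplicated pregnancies; it does not balance them against the cases. Both control groups are selected for health, so they may plausibly differ from LOPE women in age, BMI, smoking, supplement use and, among the pregnant, parity. If such a factor also relates to magnesium or vanadium, part or all of an observed difference may reflect that factor and not preeclampsia.

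Timing matters because this is a prospective plan, with recruitment from May 2020 to February 2021. A characteristic not asked at enrolment may be hard to recover, particularly for non-pregnant volunteers, for whom the plan mentions no record source. Leaving the covariates open also allows them to be chosen after the results are seen.

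**Working it through.** **1. The plan's own figure.** Inputs from section 2: d = 0.5, alpha 0.05, power 0.80. Sidedness is not stated; two-sided is assumed. For two means:

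n per group = 2 × (1.960 + 0.842)² / 0.5² = 2 × 7.85 / 0.25 = 62.8, rounded up to 63.

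This matches the stated 63; the exact t calculation gives 64. Other readings do not match: one-sided gives 50 (51 by exact t), and a three-group analysis of variance with f = 0.25 gives 53. The figure therefore fits a two-sided, two-group comparison of means with no covariates. At the planned 70 per group, power at d = 0.5 is about 84%. The sample-size figure is not in error.

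**2. Search for covariate control.** The four ways the plan could deal with confounding, and what it says on each:

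- Randomisation: none; the design is case-control.
- Matching: no matching variable is named for either control group.
- Restriction: eligibility criteria are referred to but not listed, so this cannot be judged.
- Adjustment: no model or covariate is named, and none of age, BMI, smoking, supplement use or parity is listed for recording.

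**3. Possible size of the bias (assumed inputs).** The documents give no imbalance and no correlation, so both are assumptions. Let one covariate differ by D standard deviations between two groups and correlate r with the metal level within groups, with no true LOPE effect. The unadjusted standardised difference is then about

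spurious d = D × r.

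The chance of p<0.05 is the power of a two-sided two-sample t test at this d, with 138 degrees of freedom, critical value 1.977 and noncentrality d × √(70/2) = 5.916 × d.

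| D (SD) | r | Spurious d | Noncentrality | Chance of p<0.05 |
|---|---|---|---|---|
| 0.3 | 0.2 | 0.06 | 0.355 | 6.4% |
| 0.5 | 0.3 | 0.15 | 0.887 | 14.3% |
| 0.8 | 0.3 | 0.24 | 1.420 | 29.2% |
| 0.8 | 0.4 | 0.32 | 1.893 | 46.8% |

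The nominal rate is 5%. The middle case, d = 0.15, is 0.15 / 0.5 = 30% of the effect the study is sized to detect. The table covers one covariate and one comparison; several covariates could add to or offset one another.

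**The case against.** The strongest reply is that the plan is silent, and silence is not a decision. A reader might infer from section 2 that no maternal data will be collected and that the primary analysis will be unadjusted. The documents support neither statement:

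- Some maternal data must be gathered to run the study: singleton status, gestational age at diagnosis, mild or severe LOPE, and small-for-gestational-age status.
- No analysis method is named, adjusted or otherwise. The sample-size figure fits an unadjusted comparison, but that does not fix the analysis.
- The section headings look like fields of a form, so power text under Baseline Characteristics may simply be misplaced.
- The unlisted eligibility criteria might already exclude, say, smokers or supplement users.

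All of this stands, and it limits the claim to what is not listed and not pre-specified. It does not remove the gap. Restriction cannot be assumed any more than it can be excluded, and it would not usually equalise age or BMI.

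A second reply is that section 5 already acknowledges confounding. It does, but without any step to reduce it. A third is that the false-positive rates rest wholly on assumed values. That is also true: they show what could happen, and at the low end the harm is negligible.

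**Conclusion.** The point holds as a gap in pre-specification. The plan lists no baseline covariates for any group and specifies neither matching nor adjustment, while the primary outcome rests on non-randomised groups. Followed as written, it would yield a crude contrast open to confounding.

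A reader might go further and infer that the primary result will be biased. The documents do not support that: bias arises only from a covariate that both differs between groups and relates to the metal, and the plan gives no data on either. Under the assumed values the false-positive rate runs from about 6% to 47%, with 14% in the middle case. Those figures assume a single covariate, approximate normality, 70 per group and no true effect. The change should be made, because it is cheap now and may not be possible after enrolment.

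**What to change.** **Record.** In section 2, list the variables to be recorded at the sampling visit. In all three groups: age, BMI (pre-pregnancy for pregnant women), smoking, and magnesium or multivitamin supplement use. In the two pregnant groups, add parity and gestational age at sampling; cases span 34+0 to 41+0 weeks and no window is given for pregnant controls.

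**Analyse.** Estimate both primary contrasts from linear models of metal level (log-transformed where appropriate) on group:

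- LOPE versus normal-pregnant, adjusted for age, pre-pregnancy BMI, smoking, parity and gestational age at sampling.
- LOPE versus non-pregnant, adjusted for age, BMI and smoking, with a note that this contrast also contains the effect of pregnancy itself.

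Show the unadjusted differences alongside. Add supplement use only as a sensitivity analysis: intake may itself determine the magnesium level, so conditioning on it changes the question from whether levels differ to whether they differ at equal intake.

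**Reword.** Section 5 should refer to residual confounding after this adjustment.

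**Cost.** A short enrolment form, the added models, a few degrees of freedom and some missing answers. No extra participants or procedures are needed. Any effect on the required sample size cannot be computed without covariate–outcome correlations, which the documents do not give.

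### The primary outcome covers four contrasts with no named primary contrast or success rule; if any one significant result counts, the chance of a false positive is about 16-17%

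*Combined protocol and SAP*

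**What the plan says.** Sections 3 and 4 define the primary outcome in the same words: "The primary outcome in these analyses will be compare magnesium and vanadium levels in LOPE group and the control groups". Section 1 sets out two control groups beside the 70 women with LOPE: "70 participants with normal pregnancies as control pregnant group and 70 participants with healthy volunteer women as control non-pregnant group".

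Section 2 sizes the study for one unnamed variable at Cohen's d = 0.5, alpha 0.05 and power 0.80: "minimum required sample size was estimated as 63 for each group". On analysis, it adds only the software ("SPSS for Windows 22.0 and Medcalc programs will be used for statistical analysis") and the threshold ("p<0.05$ will be accepted as statistical significance").

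The title names three specimens: "Analysis of maternal plasma/urine/hair magnesium and vanadium levels in preeclampsia". No section names a primary metal, control group or specimen, a statistical test, a testing order, a multiplicity method, or a rule for what counts as a positive primary result.

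**The concern.** Two metals and two control groups give four LOPE contrasts, all with primary status and all judged at 0.05. Two things follow.

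- **Chance findings.** With no success rule, one significant contrast out of four could be reported as the primary result. The chance that this happens when nothing differs is then well above 5%.
- **Interpretation.** Women with LOPE and non-pregnant women differ in pregnancy as well as in preeclampsia. A difference between them can come from pregnancy alone and still stand as the primary result. LOPE versus normal pregnant removes pregnancy status as an explanation. It does not remove other confounding, which Section 5 acknowledges.

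The 80% power in Section 2 applies to each pairwise test separately. It does not describe the two-metal outcome as a whole.

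**Working it through.** **Inputs from the documents.** d = 0.5, alpha 0.05, power 0.80, 63 per group (Section 2); 70 per group in three groups (Section 1); two metals and two control groups (Sections 1, 3 and 4).

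**Assumptions.** Two-sided tests, normal data, one specimen, and correlation between the metals of 0, 0.3 or 0.6. The documents give no correlation.

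**Step 1: the plan's own figure.** n per group = 2 × (1.960 + 0.842)² / 0.5² = 62.8, so 63. This reproduces the stated number as one two-sided, two-group comparison (normal approximation). The t-test version needs 64; at 63 its power is 79.5%. A one-sided test would need 50, and a three-group ANOVA with f = 0.25 about 53 per group, so neither fits.

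**Step 2: false-positive chance if any one significant contrast counts, no true differences.**

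- Within one metal, the two contrasts share the LOPE group, so with equal groups their test statistics correlate at 0.5. The chance that at least one is significant is 0.0907.
- For two uncorrelated metals: 1 − (1 − 0.0907)² = 0.173.
- For LOPE versus normal pregnant only, uncorrelated metals: 1 − 0.95² = 0.0975.

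Simulated t-tests with 70 per group give:

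| What counts as positive | r = 0 | r = 0.3 | r = 0.6 |
|---|---|---|---|
| Any of the four contrasts | 17.2% | 16.9% | 15.6% |
| Either metal, LOPE vs normal pregnant | 9.6% | 9.5% | 8.7% |
| Both metals, LOPE vs normal pregnant | 0.2% | 0.5% | 1.2% |
| Any LOPE contrast after a significant three-group F test for that metal | 8.0% | 8.0% | 7.4% |

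The first two rows are different families of tests and should not be merged into one range.

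**Step 3: power of the possible remedies, n = 70, d = 0.5, two-sided t-test.**

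- One primary metal at 0.05: 83.6%.
- At 0.025, the first Holm step: 75.5%. Reaching 80% there needs d = 0.53, or 78 per group at d = 0.5.
- Holm, both metals differ. A metal is declared if its p is below 0.025, or if its p is below 0.05 and the other metal's is below 0.025. At r = 0: 0.755 + (0.836 − 0.755) × 0.755 = 0.816. Simulation gives 81.5%, 81.0% and 80.4% at r = 0, 0.3 and 0.6.
- Holm, one metal differs. At r = 0: 0.755 + (0.836 − 0.755) × 0.025 = 0.757. Simulation gives about 76% at each r.
- Holm family error, both metals null: 4.8%, 4.9% and 4.4%.

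**The case against.** The plan never promises a 5% family-wise rate. Alpha 0.05 appears in a sample-size calculation and p<0.05 as a threshold for each test, and each test does hold 5%. This is an observational case-control study that makes no confirmatory claim. Magnesium and vanadium could fairly be treated as separate questions, with every result reported. The inflation depends on a rule that is absent from the documents and disappears if both metals must be significant. Holm also has a price: about 76% power when only one metal differs is below the plan's own target.

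Most of this stands. A reader might infer that the plan has a 17% error rate, or that it breaks a stated 5% guarantee. The documents support neither, because they do not say which results make the primary outcome positive. A reader might also multiply by three specimens: twelve comparisons would give up to about 43% if the six metal-specimen measures were independent. The documents do not say that all three specimens are primary, so that figure is not claimed.

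What does not fall away is the omission itself. Depending on the unstated rule, the same data carry a false-positive chance from under 1% to about 17%. Calling the metals separate questions would meet the multiplicity point if the plan said so, but it would not settle which control group answers the preeclampsia question. An omnibus gate is not mentioned in the plan. It would lower the rate for any LOPE contrast only to 7-8%.

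**Conclusion.** The point holds in conditional form. The missing success rule and the missing primary contrast are plain from the text. The size depends on the reading: about 16-17% if any of the four contrasts counts, and about 9-10% if only the two LOPE versus normal pregnant tests count. Both figures assume one specimen, no true differences, two-sided t-tests with 70 per group and a correlation between metals of 0 to 0.6. A stronger correlation would lower the first figure (12.6% at 0.9).

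Separately from any error rate, a difference between LOPE and non-pregnant women cannot be read as a preeclampsia finding, yet the plan gives it the same standing as the contrast with normal pregnancy. This should be changed. It does not invalidate the design, and the sample size is adequate for a single pairwise test at d = 0.5.

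**What to change.** 1. Name LOPE versus normal pregnant as the primary contrast, in one pre-specified specimen of the sponsor's choice.
2. Either apply Holm across magnesium and vanadium, or name one primary metal tested at 0.05.
3. Report the non-pregnant contrasts and the other specimens as secondary, with confidence intervals.
4. Restate Section 2 to match. For one primary metal: with 70 per group and d = 0.5, power is about 84%. For Holm: power per metal is about 80-82% if both metals differ and about 76% if only one does; 80% at alpha 0.025 needs d = 0.53.

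**Cost.** No added participants or samples are needed if the lower power is accepted. Against 83.6% for one unadjusted test, Holm loses about 2-3 points per metal if both differ and about 8 points if only one does, which falls below the plan's 80% target. Restoring 80% at the first Holm step would take 78 per group. The alternative makes one metal secondary. Either way, the non-pregnant contrasts lose primary status. Keeping all four contrasts primary with Bonferroni would cost more: 66.5% power per contrast at alpha 0.0125 with 70 per group.

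**Separate item.** Section 3 describes blood sampling and assay for other metals: "Venous blood sampled from the antecubital veins for measuring plasma concentration of cadmium, lead and vanadium levels". The primary outcome is magnesium and vanadium, so as written no magnesium assay is described. The two passages must be reconciled.
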